5. GENERAL STATISTICAL CONSIDERATIONS

5.1. Statistical Methodology

Continuous variables will be presented by descriptive statistics: n, mean, standard deviation, median, Q1-Q3, minimum, and maximum. Categorical variables will be tabulated by frequency count and percentage.

Lab results obtained from the central laboratory, rather than local laboratories, will be used for all efficacy and safety analyses. Some lab data are collected using local labs (in lieu of the ICON central lab) due to central lab kit shortages caused by the COVID-19 pandemic. In these cases, local lab values and reference ranges collected from CRFs will be integrated with central lab data when appropriate and feasible. Local lab values will be flagged in data sets and data listings to be differentiated from central lab values. Sensitivity analyses may be performed for key analyses of lab parameters without local lab values (e.g., set to missing).

Unless otherwise stated, all statistical tests will be two-sided hypothesis tests performed at the 5% level of significance for main effects and all confidence intervals will be two-sided 95% confidence intervals.

Unless otherwise specified, there will be no adjustments for multiple comparisons.

All data collected will be presented by data listings for review and substantiation of summary tables.

Safety and efficacy data will be summarized and presented by treatment group (pamrevlumab or source of external data, as applicable), and analysis visit in summary tables as appropriate.

All analyses will be performed using SAS® Version 9.4 or higher.

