9.2.2.1. Analysis Method

Annual mean change from baseline in the above efficacy endpoints each will be analyzed using Random Coefficient Model (RCM) analysis, and the estimated annual change from baseline values at year 1 through year 4 in the OLE period will be presented.

The model will include continuous variable avisityr (calculated as the elapsed days of assessment date from baseline date in the unit of year) and baseline endpoint as fixed effects, while the intercept and avisityr are included as random effects.

The unstructured covariance structure for the within-patient errors in the model will be applied first. The by-treatment-group option is included to the covariance pattern to improve the model efficiency.

If the algorithm for unstructured covariance pattern does not converge, the following covariance structures will be tested in sequence until the model converges: heterogeneous Toeplitz, homogeneous Toeplitz, first-order autoregressive, compound symmetry, and variance component. The sandwich estimator will be used if there is convergence issue. If the model does not converge for all covariance structures listed above, some least significant factors or interaction terms ($p>0.05$)

can be excluded from the model to achieve convergence. The revised model with fewer factors or interaction terms will be tested using the same sequence as specified above.

When the random effects model does not converge or do not have a positive definite Hessian, the fixed effects instead of random effects for the intercept and slope will be performed instead.

The LSMean (SE) and 95% CI for annual change (slope) as well as estimated changes from baseline at year-1, year 2, year 3 and year 4 (regarding week 52, week 104, week 156 and week 208) will be presented.

9.2.2.2. Handling of Intercurrent Events:

Treatment discontinuation (such as: due to AEs, Lost to Follow-Up, Withdrawal by subject, Physician Decision, Protocol Deviations, etc.): treatment policy: the occurrence of the intercurrent event is irrelevant. All observed values will be used regardless of whether or not the inter-current event occurs.

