9.2.4. Exploratory Analysis - Comparison with the CINRG natural history data

Efficacy endpoints: % predicted FCV (ppFVC), LVEF, and grip strength in dominant hand will be compared with a subset of CINRG DMD Natural History study (DNHS) data with all 36 subjects using a random coefficient model (RCM). The other outcome measures including Performance of Upper Limb (PUL), cardiac fibrosis by LGE, and Myocardial Circumferential Strain [Mean Peak Circumferential strain (MPCS) and Global Circumferential Strain (GCS) percentage] assessed by cardiac MRI are not available in CINRG data and therefore will not be compared.. The RCM model will use efficacy data from both the main and OLE periods and include continuous variable avisityr (calculated as the elapsed days of assessment date from main study baseline date in the unit of year), treatment trt (079 subjects as treated with trt = 1, and subjects in CINRG data as control with trt =0), the interaction term of trt and avisityr, and baseline endpoint as fixed effects, while the intercept and avisityr are included as random effects. The strategy for covariance structure for the within-patient errors in the model is the same as what is described in [Section 9.2.2.1](#). The LSMean (SE) for annual change (slope) as well as LSMean (SE) and 95% CI of treatment differences between pamrevlumab and control of estimated changes from baseline at year 1, year 2, year 3 and year 4 in the OLE period will be presented. The sample SAS code is provided in [Appendix 2](#).

Line plots of each subject's efficacy trajectory compared with the mean plot of the CINRG will be provided.

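### If the random coefficient model fails, the OLE SAP falls back to fixed effects without saying that subject clustering is kept, so some 95% CIs can be much too narrow

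*SAP*

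**What the plan says.** SAP 9.2.2.1 fits change from baseline on time in years and baseline value, "while the intercept and avisityr are included as random effects". It then gives three provisions for trouble:

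- **A sequence of simpler structures.** If the unstructured pattern does not converge, the analyst tries "heterogeneous Toeplitz, homogeneous Toeplitz, first-order autoregressive, compound symmetry, and variance component", and after that may drop non-significant terms.
- **A variance estimator.** In the same paragraph: "The sandwich estimator will be used if there is convergence issue".
- **The fallback, in a separate paragraph.** "When the random effects model does not converge or do not have a positive definite Hessian", then "the fixed effects instead of random effects for the intercept and slope will be performed instead".

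The outputs do not change under the fallback: "The LSMean (SE) and 95% CI for annual change (slope) as well as estimated changes from baseline" at years 1 to 4. SAP 5.1 sets two-sided 95% intervals. The sample code in SAP Appendix 2 shows random-effects models only. The subject identifier appears only in the RANDOM statements (and CLASS), and there is no empirical-variance option.

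**The concern.** The model already contains a fixed intercept and a fixed time slope. Replacing the random effects by fixed ones can therefore mean two things, and the SAP does not say which:

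- **Pooled fit:** the RANDOM statement is deleted, leaving one common line. In the Appendix 2 code nothing would then link visits of the same subject.
- **Subject-specific fit:** each subject gets his own fixed intercept and slope, and these are averaged. The SE then reflects residual error only, as if these subjects were the whole population.

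With model-based SEs, neither interval is valid for the mean decline in the population. At stake is how precise the long-term estimates look, the later-year changes above all.

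**Working it through.** **The plan's own figure.** The documents give no figure for the OLE or for the fallback. The only design figure is the main study's 22 subjects (Protocol 9.1). The normal formula reproduces it: n = [5 × (1.960 + 0.842) / 3]² = 21.8, so 22. (With the exact noncentral t, power at 22 is 76.5%.) It serves here only as a plausible N. The protocol's SD of 5% is not split into between-subject and residual parts.

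**Inputs from the documents.** Main-study PFT visits at weeks 12, 24, 36, 48, 60, 72, 84 and 104 (Protocol Appendices 1 to 3). OLE PFT every 24 weeks, 8 visits to week 192, and cardiac MRI at weeks 52, 104, 156 and 208 (Protocol Appendix 6). Unless otherwise noted, efficacy runs from the main-study baseline to the last extension visit (SAP 9.2).

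**Assumed.** N = 22, residual SD σ = 5, between-subject slope SD τ = 3 points per year, complete data, OLE start at week 104.

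**Formulas.** K visits at times t (years), S = Σ(t − t̄)², g = 1/K + (4 − t̄)²/S. Change from baseline carries the baseline error at every visit, so the pooled residual variance is about V = 2σ² + τ² × mean(t²).

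- Slope, true SE: √[(τ² + σ²/S)/N]
- Slope, pooled model-based SE: √[V/(N·S)]
- Slope, subject-specific model-based SE: σ/√(N·S)
- Year-4 change, true SE: √[(16τ² + σ²(1 + g))/N]
- Year-4 change, pooled model-based SE: √[V·g/N]
- Approximate coverage: 2Φ(t-quantile × model SE / true SE) − 1, t-quantile 1.97 for PFT and 1.99 for MRI

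**ppFVC, main plus OLE visits** (K = 16, t̄ = 2.56, S = 47.6, mean t² = 9.52, g = 0.106, V = 50 + 9 × 9.52 = 135.7):

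- Slope: true √[(9 + 25/47.6)/22] = 0.658; pooled √[135.7/(22 × 47.6)] = 0.360, coverage about 72%; subject-specific 5/√(22 × 47.6) = 0.155, coverage about 36%.
- Year 4: true √[(144 + 25 × 1.106)/22] = 2.79; pooled √[135.7 × 0.106/22] = 0.81, coverage about 43%.

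**Annual MRI** (K = 4, t̄ = 2.5, S = 5, mean t² = 7.5, g = 0.70, V = 50 + 9 × 7.5 = 117.5):

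- Slope: true √[(9 + 5)/22] = 0.798; pooled √[117.5/110] = 1.034, so too wide; subject-specific 5/√110 = 0.477, coverage about 77%.
- Year 4: true √[(144 + 25 × 1.70)/22] = 2.91; pooled √[117.5 × 0.70/22] = 1.93, coverage about 81%.

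**Simulation at the same inputs** agrees. For the pooled fit it gives coverage of 69% (PFT slope), 44% (PFT year 4) and 80% (MRI year 4). For the subject-specific PFT slope it gives 35%.

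**Range over the assumptions** (balanced data, N = 22 and 12, σ = 3 and 5, τ = 0 to 5):

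| Estimate | Pooled, model-based | Subject-specific, model-based |
|---|---|---|
| Year-4 change, all schedules | 34–91% | 8–82% |
| ppFVC slope, main + OLE visits, τ ≥ 1 | 59–91% | within 13–94% |
| ppFVC slope, OLE visits only | 85–98% | within 13–94% (τ ≥ 1) |
| MRI slope | 96–99% | within 13–94% (τ ≥ 1) |

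The subject-specific slope range of 13–94% is for all schedules together with τ ≥ 1. With τ = 0 the pooled slope CI is too wide: 1.18 to 1.32 times the width of an interval that keeps between-subject variance. A separate simulation with 21 subjects gave, for the pooled fit, 35–86% for year 4, 49–75% for the ppFVC slope with main and OLE visits, and 91–97% for the MRI slope.

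**With a subject-level sandwich on the pooled fit:** 90–96% in the balanced runs and 90–94% with 21 subjects.

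**The case against.** Four points on the other side are fair.

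- **The sandwich sentence may already cover this.** Non-convergence is a convergence issue, so a plain reading lets the sandwich apply, and coverage is then close to nominal. This stands as far as it goes. But the sentence belongs to the paragraph on covariance structures, does not mention the Hessian, names no clustering unit or small-sample version, and has no counterpart in the sample code.
- **The fallback is a last resort.** True for non-convergence, where the sequence of structures comes first. For a fit that converges with a non-positive-definite Hessian, the text names no intermediate step.
- **The error is not always towards narrowness.** A reader might infer that the fallback always makes intervals far too narrow. It does not: the pooled slope CI is about right or too wide for annual MRI, and too wide when slopes barely vary.
- **There are other OLE results.** SAP 9.2.1 gives descriptive summaries with CIs, and SAP 9.2.3 gives MMRM changes for several endpoints. Its list does not include ppFVC, although SAP Section 13 names it.

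Three stronger readings are not supported:

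- **That the trigger is common.** The available rates are proxies. A non-positive-definite moment estimate occurred in at most 2% of runs for main plus OLE spirometry (N = 22, τ ≥ 1) and in 16–44% for four annual MRIs. Boundary estimates of 9–36% (spirometry) and 31–54% (MRI) concern the unstructured fit only. None of these counts arrivals at the fallback.
- **That it governs the natural-history comparison.** SAP 9.2.4 says only: "The strategy for covariance structure for the within-patient errors in the model is the same as what is described in" 9.2.2.1. Whether the fixed-effects step comes with that is inference.
- **That it threatens the trial's primary conclusion.** This SAP covers the extension, which has no success rule and which Protocol Appendix 6 treats as descriptive.

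**Conclusion.** The point holds as a conditional one. The fallback rule is in the SAP, it removes the terms that carry between-subject variation, and the intervals are still promised. If model-based SEs are used:

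- the year-4 change CI is too narrow on every schedule examined (pooled-fit coverage roughly 35–90%);
- the ppFVC slope CI is too narrow when main and OLE visits are pooled and slopes vary (roughly 50–90%);
- the pooled slope CI for annual MRI endpoints is about right or too wide.

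A subject-level sandwich largely repairs this (about 90–96%), but the SAP leaves open whether it applies to the fixed-effects fit or to the Hessian trigger. The sizes rest on assumed values of τ and σ, about 21 to 22 subjects and normal errors; none of these is given for the OLE. The direction for the year-4 change did not depend on which values were tried. The main-study criterion (lower 95% bound above -5%) is unaffected.

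**What to change.** Replace the fallback sentence in SAP 9.2.2.1 so that:

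1. a non-positive-definite Hessian, like non-convergence, first goes through the simpler random-effects structures: variance components (intercept and slope uncorrelated), then a single random effect;
2. if none works, the fixed-effects mean model (common intercept, time and baseline) is fitted with a subject-level sandwich variance, small-sample-corrected, with degrees of freedom based on the number of subjects, for the slope and for the year 1 to 4 changes;
3. model-based SEs that ignore subject clustering are not reported.

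The mean of per-subject least-squares slopes with a one-sample t interval may support the slope. It cannot replace step 2, because it gives no year 1 to 4 changes and needs at least two values per subject.

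The cost is SAP wording, a few lines of code, and generally wider intervals when the fallback is used.

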9.2.3. Change from Baseline in Efficacy Endpoints with MMRM

The following efficacy endpoints will be analyzed with MMRM method.

1. At Week 48, Week 96, Week 144, and Week 192
 - a. Change from baseline in PUL total score, including middle and distal score
 - b. Change from baseline in grip strength. The grip strength should be reported by dominant and non-dominant hand separately.
2. At Week 52, Week 104, Week 156, and Week 208
 - a. Change from baseline in LVEF%
 - b. Change from baseline in cardiac MRIs including cardiac fibrosis score assessed by Late Gadolinium Enhancement (LGE)
 - c. Change from baseline in Myocardial Circumferential Strain [Global Circumferential Strain (GCS)]

9.2.3.1. Analysis Method

The observed and change from baseline in the above efficacy endpoints each will be summarized by analysis visit and analyzed using MMRM with visit, baseline, and age with appropriate covariance matrix for the within subject covariance over time.

If the algorithm for unstructured covariance pattern does not converge, the following covariance structures will be tested in sequence until the model converges: heterogeneous Toeplitz, homogeneous Toeplitz, first-order autoregressive, compound symmetry, and variance component. The sandwich estimator will be used if there is convergence issue. If the model does not converge for all covariance structures listed above, some least significant factors or interaction terms ($p>0.05$) can be excluded from the model to achieve convergence. The revised model with fewer factors or interaction terms will be tested using the same sequence as specified above.

9.2.3.2. Handling of Intercurrent Events:

Treatment discontinuation (such as: due to AEs, Lost to Follow-Up, Withdrawal by subject, Physician Decision, Protocol Deviations, etc.): treatment policy: the occurrence of the intercurrent event is irrelevant. All observed values will be used regardless of whether the inter-current event occurs.

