## 1. PROTOCOL SYNOPSIS

Study Title:	Trial of Pamrevlumab (FG-3019), a Monoclonal Antibody to Connective Tissue Growth Factor, in Non-Ambulatory Subjects with Duchenne Muscular Dystrophy
Protocol Number:	FGCL-3019-079, Amendment 8.0
Investigational Product:	Pamrevlumab (FG-3019) (Recombinant fully human IgG1 kappa monoclonal antibody to connective tissue growth factor)
Study Phase:	Phase 2
Target Population:	Non-ambulatory subjects with Duchenne muscular dystrophy (DMD)
Number of Subjects Planned:	Approximately 22 subjects will be enrolled; interim analysis may increase sample size to approximately 32
Study Centers Planned:	Approximately 10 centers

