#### **7.1.4. Early Withdrawal from Treatment and Safety Follow-up Period**

Subjects who prematurely discontinue the main study should be strongly encouraged to complete the final efficacy evaluations scheduled for Week 208/EOT as applicable, and the safety follow-up evaluations scheduled for the Week 210/EOS visit (4 weeks following the last dose).

Subjects who withdraw prior to week 104 will not be eligible to participate in the OLE.

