## 9. STATISTICAL CONSIDERATIONS

### 9.1. Sample Size Determination

This study tests the hypothesis of whether pamrevlumab can attenuate the annual decline from baseline to Week 104 in FVC in non-ambulatory DMD patients. A total of 22 subjects is planned to achieve 80% power to test the null hypothesis of change in percent predicted FVC of -5% against the alternative hypothesis, assuming a mean change of -2% and standard deviation of 5% based on 2-sided one sample t-test at 0.05 significance level. The hypotheses are:

H0: change in percent predicted FVC less than or equal to -5%

Ha: change in percent predicted FVC greater than -5%.

The primary efficacy endpoint will be met if the annual change in percent predicted FVC is greater than -5% at the end of the study (lower bound of 2-sided 95% confidence interval is greater than -5%).

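### The SAP uses the sandwich variance as a response to non-convergence, which it cannot cure, and names no small-sample correction or degrees of freedom for it

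*SAP*

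**What the plan says.** SAP 9.2.3.1 has change from baseline "analyzed using MMRM with visit, baseline, and age with appropriate covariance matrix". If the unstructured covariance fails, five simpler structures are tried in order: heterogeneous Toeplitz, homogeneous Toeplitz, AR(1), compound symmetry (CS) and variance components (VC). The next sentence is "The sandwich estimator will be used if there is convergence issue". After that, non-significant terms may be dropped. SAP 9.2.2.1 has the same sequence and the same sentence for the random coefficient model (RCM).

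Neither section names a sandwich variant, a small-sample correction, degrees of freedom, or the step at which the sandwich enters. SAP 5.1 sets the standard the results should meet: "all confidence intervals will be two-sided 95% confidence intervals". In SAP Appendix 2 both code samples are PROC MIXED. The single-arm RCM sample has TYPE=CS and no DDFM option. The external-control sample has TYPE=UN and DDFM=KR. Neither requests a sandwich.

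On sample size, Protocol 9.1 says "A total of 22 subjects is planned to achieve 80% power" and the synopsis adds "interim analysis may increase sample size to approximately 32". Protocol 7.1.4 limits entry to the extension: "Subjects who withdraw prior to week 104 will not be eligible to participate in the OLE". Neither document gives the number of subjects in the extension.

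**The concern.** There are two problems.

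First, the remedy does not fit the fault. Non-convergence is a failure to estimate the covariance parameters. The sandwich takes a completed fit and replaces the variance of the fixed-effect estimates, so it leaves the failure where it was.

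Second, the sandwich is justified by a large number of independent subjects. With few subjects the ordinary form is biased downward, because the fitted residuals are smaller than the true errors. An unstructured fit is most likely to fail with few subjects and thin late visits, which is also where the ordinary sandwich is least reliable.

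At stake is the width of the intervals for PUL, grip strength, LVEF, LGE fibrosis score and circumferential strain, and for the RCM slopes including ppFVC.

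**Working it through.** **1. The plan's own figure, for scale.** Inputs from Protocol 9.1: "assuming a mean change of -2% and standard deviation of 5" percent, null -5%, "2-sided one sample t-test at 0.05 significance level". The difference is 3. By the normal formula, n = (5 × (1.960 + 0.842) / 3)² = 4.67² = 21.8, so 22, as stated. The exact t calculation gives 24, and exact power at 22 is 76.5%. That is a separate matter. Here 22 only sets the scale of the study.

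**2. How easily the fallback is reached.** With four visits, an unstructured covariance has 4 × 5 / 2 = 10 parameters. The mean model has 4 + 1 + 1 = 6. Fitting these to about 22 subjects or fewer, with missing data not imputed (SAP 5.3), makes failure realistic. Its probability is unknown.

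**3. Simplest case, in closed form.** With one visit and no covariates, the uncorrected sandwich SE of a mean is (s/√n) × √((n-1)/n). With z, coverage is P(|T(n-1)| < 1.96 × √((n-1)/n)):

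| n | 1.96 × √((n-1)/n) | Coverage |
|---|---|---|
| 10 | 1.859 | 90.4% |
| 15 | 1.894 | 92.1% |
| 20 | 1.910 | 92.9% |
| 22 | 1.915 | 93.1% |

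Covariates and dropout lower these values.

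**4. The four-visit MMRM, simulated.** The model has visit, baseline and age, fitted by REML. Assumptions not in the documents:

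- Setting A: true covariance heterogeneous autoregressive (correlation 0.6, SD 3 to 6); dropout leaving about 60% at visit four; working CS or VC; 3,000 data sets per cell.
- Setting B: true covariance either random intercept and slope, or CS with correlation 0.6; dropout 5-20% per year; working CS, AR(1) or VC; 1,500-2,000 data sets per cell (Monte Carlo error about 0.5-1 point).

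Coverage of the nominal 95% interval, uncorrected sandwich, last visit:

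| n | A, residual df | B, z or within-subject df |
|---|---|---|
| 10 | 83-85% | 84-88% |
| 15 | 88-90% | 88-90% |
| 20 | 90-91% | 90-92% |
| 22 | not run | 91-92% |
| 32 | not run | 93-94% |

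A third run of the same four-visit model gave 82-86%, 87-90% and 91-92% at 10, 15 and 20. With t(n-3), coverage at 10 to 20 subjects is 88-93% in A and 90-93% in B. The first visit is milder: 91-94% at n = 20 in B, with z or within-subject df.

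**5. Size of the SE error.** In A at n = 20 with CS, the true SE is 1.71 and the mean uncorrected sandwich SE is 1.53. The ratio is 1.53 / 1.71 = 0.89, about 11% too small. The mean corrected SE is 1.74.

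**6. With a correction.** A Mancl-DeRouen correction with t(n-3) gives 95-96% in A. In B, CR2 with t(n-3) gives about 93-97.5% for n = 8 to 20, and CR3 with within-subject df gives about 94-95.5% at the last visit for n = 10 to 20.

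**7. RCM slope.** In B, the uncorrected sandwich with z or residual df covers 89-91.5% at n = 10, 90-91% at 15 and 92-92.5% at 20; t(n-1) gives 92-94.5%. Simulated under A's separate RCM runs (4,000 data sets per n), z gives 90% at 10 and 93% at 15-20.

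**8. Comparator without a sandwich.** In B, when the truth is a random slope and a simpler structure is fitted, model-based intervals cover about 78-88% at the last visit. When CS is the true structure, they cover about 92-96% (n = 12 to 20).

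**The case against.** The sentence can be read charitably. Once a simpler structure replaces unstructured, a sandwich SE is a sensible guard against having chosen the wrong one. Step 8 bears this out: with a wrong structure, even the uncorrected sandwich covered better at the last visit than model-based SEs. This stands, and it is why the fix keeps the sandwich and corrects it.

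A reader might infer that the SAP applies an uncorrected sandwich to 20 or fewer subjects and so delivers 85-91% coverage. The documents do not support that:

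- The SAP is silent on the variant, so uncorrected is a reading of that silence.
- The extension sample size is not given, and about 32 subjects were possible in the main study.
- Coverage near 85% belongs to about 10 subjects at the last visit with z or residual df.
- CS and VC come last in the fallback order. Heterogeneous Toeplitz comes first and was not simulated. It contains the true covariance used in Setting A.

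Nor do the figures carry over to the external-control comparison in SAP 9.2.4. It borrows the covariance strategy of 9.2.2.1, but it adds external subjects and its sample code uses Kenward-Roger.

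Finally, the impact is limited. Protocol Appendix 6, section 5 calls for a descriptive summary of extension data, SAP 13 lists the MMRM as an additional analysis, and no extension success criterion rests on a confidence limit. All of this stands. What remains is a rule that cannot do what it is invoked for, and a variance method left open where the choice matters.

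**Conclusion.** The concern holds in a limited form. The sandwich is offered for a problem it cannot solve, and without the correction and degrees of freedom it needs with few subjects.

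If the ordinary form is used, last-visit MMRM intervals labelled 95% cover about 82-88% at 10 subjects, 87-90% at 15 and 90-92% at 20 with z or residual df, or about 88-93% with t(n-3). The loss is small by about 30 subjects. These figures rest on assumed extension numbers, dropout and covariance, and on AR(1), CS or VC as the working structure.

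The rule operates only when the unstructured fit fails. Changing the variance estimator leaves the point estimates alone, so a reader should not infer that the estimated long-term change itself is biased. Only its stated precision is affected. The main-study test against -5% falls under a separate SAP and is not touched. The change should be made, but it does not threaten the trial's main conclusion.

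**What to change.** In SAP 9.2.2.1 and 9.2.3.1, replace the sandwich sentence with wording such as:

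> When the unstructured model converges, inference will use model-based REML with DDFM=KR. Whenever a simpler covariance structure is used, standard errors will come from a small-sample bias-corrected sandwich (for example Mancl-DeRouen or CR2 type), with t degrees of freedom equal to the number of subjects minus the number of subject-level parameters.

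Convergence itself is then left to the sequence of structures. The single-arm RCM code in Appendix 2, which starts at CS, should be aligned with the text, which starts at unstructured. Mancl-DeRouen and CR2 are both acceptable, provided one is named in advance.

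The cost is SAP wording, a different procedure option (for example PROC GLIMMIX with EMPIRICAL=FIRORES) and wider intervals. In the 20-subject CS run of Setting A, the half-width goes from 1.96 × 1.53 = 3.00 (uncorrected, z) to 2.11 × 1.74 = 3.67 (corrected, t with 17 df). That is the width needed for about 95% coverage in that setting.
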